5.4. Tumour Biopsies, Archival Tissue Collection & Correlative Blood Studies

5.4.1. Archival Tumour tissue samples - MANDATORY

Archival tissue samples will be collected all participants that have consented and have available samples. FFPE tumour blocks will be requested and where it is not possible to obtain the whole block, 10-15 slides freshly prepared unstained 5 micron sections may be provided instead. Archival tumour blocks will be returned to source at the end of the study or, upon request, earlier if required for the participant's clinical management. Cut sections will be retained by the study team. These are archived samples and as such participating participants will not need to attend extra visits or undergo extra procedures.

5.4.2. Diagnostic Metastatic Tumour Biopsy - MANDATORY

All participants will be required to consent to a diagnostic metastatic tumour biopsy during screening to confirm the presence of metastatic disease. If the participant has already had a biopsy of a metastatic lesion (stage 4) there is no requirement to repeat this. In addition, participants will be also asked to consent for this biopsy to be used in the exploratory endpoint analysis as described in section 5.4.3.2.

5.4.3. Tumour Tissue Collection and Correlative Studies Blood Sampling - OPTIONAL

Exploratory immunological endpoints will be determined from peripheral bloods and from tumour biopsy samples. Participants will be asked to consent to both tumour biopsy and blood collection to take part in this exploratory research.

5.4.3.1. Peripheral Blood Analysis

[figure not shown]
Consenting participants will be asked to provide an additional 50ml of blood at each visits prior to the administration of pembrolizumab for the first 12 weeks of treatment and a further blood sample at either time of response or progression (to be determined by the relevant clinician). Detailed processing procedures will be provided in a separate laboratory trial manual. These additional research bloods are considered to be research samples and will be retained under the PERM Trial ethics until used for analysis or destroyed following completion of the trial. All samples will be analysed to assess immune function in response to pembrolizumab ± radiotherapy. Assays to examine innate and/or adaptive immune functional response may include, for example, immunophenotyping, cytokine/chemokine arrays. For details, refer to the associated Trial Manual.

5.4.3.2. Tumour Biopsy Samples

For consenting participants post treatment biopsies will be taken at their second cycle of pembrolizumab ideally from the same lesion that was used to confirm metastatic disease at screening. If this biopsy was from a

lesion that had been irradiated then if possible an additional biopsy outside the radiotherapy field should also be collected. Biopsies will be core or punch biopsies. Detailed processing, handling and shipping procedures for these biopsies will be provided in a separate laboratory trial manual. These additional tissue biopsies are considered to be research samples and will be retained under the Manchester Cancer research Centre.

Tumour biopsy tissue collected from patients at baseline & during treatment will be examined to assess the tumour microenvironment in response to therapy. Tumour may be used in, for example, multi-colour immunohistochemistry and RNA sequence analysis to investigate TIL infiltration & expression of known tumour-associated antigens. For details, refer to the associated Trial Manual.

*Ideally from the same lesion that was used to confirm metastatic disease at screening. If this biopsy was from a lesion that had been irradiated then if possible an additional biopsy outside the radiotherapy field should also be collected.

Figure 3: Blood and tumour sampling schedule.

5.4.4. Chain of Custody of Biological Samples

In all cases, participants will be consented for the collection and use of their biological samples and a full chain of custody will be maintained for all samples throughout their lifecycle. The Investigator at each site is responsible for maintaining a record of full traceability of biological samples collected from participants while these are in storage at the site, either until shipment or disposal. Anyone with custody of the samples e.g. sub-contracted service provider will have to keep full traceability of samples from receipt to further shipment or disposal (as appropriate).

RM-CTU will keep overall oversight of the entire lifecycle through internal procedures and monitoring of study sites. Tissue samples retained for further use will be registered with the Manchester Cancer Research Centre and research blood samples retained for further use under the PERM trial ethics.

5.5. Total Blood Volume

The total volume of blood that will be drawn from each trial participant for the assessments described in the sections above is shown in Table 5.

	Sample volume (mL)	No. of samples	Total volume (mL)
Routine Haematology	6	18 ¹	108
Routine Clinical chemistry	8	18 ¹	144
Total Routine			252
Peripheral Blood Sampling (Optional)	50	5	250
Total:			502²

Table 6: Total Volume of blood

To be drawn from each trial participant for the duration of the trial; calculations based on 1 year on treatment, plus end of treatment visit and 30 days post end of treatment safety visit (where applicable).

Blood volumes for haematology and clinical chemistry may vary according to local practice

² The total volume of blood drawn from each trial participant for the duration of the trial depends on the time to progression for each participant.

6.0. STUDY TREATMENT

6.1. Trial Treatment

Participants will be randomised to receive either pembrolizumab alone or pembrolizumab and high dose radiotherapy. **Images will be reviewed centrally by the Radiotherapy Quality Assurance team to ensure consistency in reviewing images².** The doses to be administered are:

1. **Pembrolizumab 200mg** every 3 weeks by intravenous infusion until progression, intolerance or withdrawal.
2. **High dose radiotherapy**, 24Gy in 3 fractions over 3 consecutive days to a deposit of melanoma after the first and before the second pembrolizumab infusion is given. Radiotherapy will be targeted at one or more suitable lesions (maximum of 3). At least one of the lesions will be left un-irradiated and will serve as the index lesion for subsequent evaluation.

6.2. Standard of Care Treatment – Radiotherapy³

6.2.1. Timing of radiotherapy

Radiotherapy (RT) should begin after the first and before the second dose of pembrolizumab. For participants due to receive RT to their internal metastases, radiotherapy planning should commence as soon as they have been recruited into the study to allow adequate time for prospective case reviews and feedback of radiotherapy plans.

6.2.2. Sites suitable for radiotherapy

Participants must have at least two sites of metastatic disease from their primary melanoma. One of the metastatic sites will serve as the index lesion for subsequent assessment of the abscopal effect and should not receive RT. A maximum of 3 Lesion(s) can be irradiated and must be at least 1 cm but no more than 5 cm in size, as measured by its widest dimension on CT scan (for internal lesions) or on clinical inspection (for superficial lesions). Metastatic lesions must not be an intra-cranial, intra-ocular lesion or intra-mesenteric lesion to receive RT. The choice of the lesion(s) to be irradiated will be left to the discretion of the attending oncologist, taking into account the Organs At Risk (OAR) normal tissue tolerance constraints associated with irradiating each lesion, and importantly the ease of obtaining pre and post radiotherapy biopsies from the index lesion(s) for the associated translational study. For example, if there is one internal and one superficial

² Patients will be consented to allowing their images to be sent outside of their institution. Please refer to the current Radiotherapy Imaging Manual for further guidance

³ Further information on this section is available in the current Radiotherapy QA Guidelines Manual which will be provided by the trials office

lesion, it may be preferable to irradiate the internal lesion so that biopsy can be taken from the superficial lesion pre and post irradiation.

6.2.3. Radiotherapy techniques

Appropriate radiotherapy techniques should be used to ensure dose coverage of the irradiated lesions and to respect the organs at risk constraints as specified (see the current Radiotherapy QA Guidelines Manual for further information). It is envisaged that the majority of metastases to be irradiated will be those on the skin and in the superficial nodes, in which case either electron or 3D conformal radiotherapy can be used. The attending oncologist may choose to irradiate metastases in the liver, lung, para-vertebral region or deep seated nodes. In these cases complex IMRT or SBRT techniques may be appropriate and will be permitted.

As the radiotherapy fractionation schedule employed for this trial, 24Gy/3# is not a recognised palliative dose for melanoma at present, and giving it concurrently with Pembrolizumab is not the standard of care, maintaining the safety of patients recruited into the study should be our absolute priority. Therefore only CtE SABR centres with established clinical experience in irradiating sites close to critical organs at risk (such as mediastinal lymph nodes, thoracic oligometastases, hepatic metastases and paravertebral soft tissue metastases) in their routine clinical practice should irradiate these targets in this trial. Patient recruited at sites which are non-SARB CtE centres, patients will still receive pembrolizumab locally at the site but may be irradiated at other CtE centre.

It is anticipated that for centres with limited experience in delivering SABR, cutaneous metastases or superficial lymph nodes would be the most common targets for radiotherapy in this study.

6.2.4. Radiotherapy Dose

Lesion(s) will be irradiated to the dose of 24Gy in 3 fractions delivered over 3 consecutive days in cycle 1.

6.2.4.1. Radiotherapy Quality Assurance

The QA programme for the study will be designed and implemented by the NCRI Radiotherapy Trials QA (RTTQA) Group. The programme will compose pre-trial and on-trial QA components to ensure adherence to protocol requirements.

6.2.4.2. Pre-Accrual QA

1. Facility Questionnaire

Participating centres will be asked to complete a facility questionnaire on general and trial specific questions on recent independent audit history, equipment, software and techniques to be used for the trial.

2. Process Document

Participating centres will be asked to submit a process document, detailing the entire radiotherapy planning chain for all of the radiotherapy techniques to be used by the site in this trial.

3. Dummy run

Participating centres may be asked to export a centre participant planned and treated according to the trial protocol. The outlining and planning for this case will be independently reviewed in terms of protocol adherence.

6.2.4.3. IMRT and SABR use for the trial

All centres intending to use IMRT techniques must be IMRT credentialed through the RTTQA group or accepted equivalent. Further information on this process is available at www.rtrialsqa.org.uk. Those centres intending to use SABR techniques, to irradiate internal metastatic lesions, must have completed the UK SABR audit.

6.2.4.4. On Trial Quality Assurance

1. **Plan Assessment Form:** An electronic copy of the plan assessment form containing key treatment details must be completed and submitted for all participants. These will be reviewed prospectively for all participants.
2. **Export of electronic data:** structure sets, dose and plan data for all recruited participants to be exported to the RTTQA group.
3. **Prospective (real time) review:** For participants with internal metastases: all cases will be participant to prospective review of outlining and planning.
4. **For all other cases:** prospective review of the Plan Assessment Form only.

Non-compliance of outlining or planning for the trial will be highlighted to the Chief Investigator (CI) and local Principal Investigators (PIs) and appropriate action taken.

6.3. Trial Treatment - Pembrolizumab

6.3.1. Investigational Product

The Investigational Medicinal Product (IMP) for this study is Pembrolizumab. A potent and highly-selective humanized mAb of the IgG4/kappa isotype designed to directly block the interaction between PD-1 and its ligands, PD-L1 and PD-L2. Pembrolizumab potentiates existing immune responses only in the presence of antigen and does not non-specifically activate T-cells.

Pembrolizumab will be manufactured by MSD according to Good Manufacturing Practice and will be provided in the formulation as described in Table 6. Additional information about the investigational product can be found in the current Investigator's Brochure (IB).

Product Name & Potency	Dosage Form
Pembrolizumab 50 mg	Lyophilized Powder for Injection

Table 7: Product Description

6.3.2. Product Preparation

The powder for infusion is a sterile, non-pyrogenic lyophilized powder for intravenous infusion supplied in single-use Type I glass vial containing 50mg of pembrolizumab. The product is preservative-free, white to off-white powder and free from visible foreign matter.

The powder will need to be reconstituted with 2.3 mL sterile water for injection (WFI) to yield a 2.4 mL solution containing 25 mg/mL of pembrolizumab at pH 5.2 – 5.8. Each vial contains an excess fill of 10 mg (equivalent to 0.4 mL of reconstituted solution) to ensure the recovery of label claim of 50 mg MK-3475 per vial (equivalent to 2.0 mL of reconstituted solution).

6.3.3. Storage and Handling

6.3.3.1. Storage

The original powder for infusion should be stored at refrigerated conditions (2 – 8°C). Prior to reconstitution, the vial can be out of refrigeration (temperatures at or below 25°C (77°F)) for up to 24 hours.

Prepared infusion solutions may be stored at room temperature for a cumulative time of up to 4 hours. This includes room temperature storage of reconstituted drug product solution in vials, room temperature storage of admixture solutions in the IV bags and the duration of infusion. In addition, reconstituted vials and/or IV bags may be stored under refrigeration at 2°C to 8°C (36°F to 46°F) for up to 20 hours. If refrigerated, allow the vials and/or IV bags to come to room temperature prior to use.

6.3.3.2. Handling

Infusion solutions should be prepared in **0.9% Sodium Chloride Injection, USP** (normal saline) or regional equivalent and the final concentration of pembrolizumab in the infusion solutions should be between 1.0 mg/mL and 10.0 mg/mL. If normal saline is not available, 5% Dextrose Injection, USP or regional equivalent

(5% dextrose) is permissible, Please note, the preferred diluent is 0.9% Sodium Chloride and 5% dextrose is only permissible if normal saline is not available.

Pembrolizumab should **NOT** be mixed with other diluents unless instructed by the sponsor in writing.

Parenteral drug products should be inspected visually for particulate matter and discoloration prior to administration. Discard the drug product vial if extraneous particulate matter other than translucent to white proteinaceous particles is observed. Sites should follow their SOPs for drug transport and delivery, with all possible effort to minimize agitation of the reconstituted drug product between the pharmacy and the clinic.

DO NOT:

- **Use if discoloration is observed**
- **Shake or freeze the vial(s)**
- **Administer the product as an (intravenous (iv) push or bolus)**
- **Combine, dilute or administer it as an infusion with other medicinal products**
- **Co-administer other drugs through the same infusion line**

Further details on the preparation of the drug product can be found in the IMP handling guidelines.

At each site the Investigator / designee e.g. pharmacist is responsible for ensuring that all trial medication is stored in a secure, limited-access location under the storage conditions specified on the label. Receipt and dispensing of trial medication must be recorded by an authorized person at the trial site. Trial medication may not be used for any purpose other than that stated in the protocol.

6.3.4. Supply, Packaging and Labelling Information

Pembrolizumab will be supplied by Merck, Sharp and Dohme (MSD) as lyophilized powder for injection. Pembrolizumab will be packaged, labelled and delivered to the participating sites by MSD. The IMP will be supplied specifically for the trial and should not be used for any other purpose than that stated in this protocol. The drug will be labelled in accordance to Good Manufacturing Practice Annex 13. As a minimum the labels will include the following information;

- a. name of the Sponsor
- b. name of drug, dose, quantity of dose units and route of administration
- c. batch number to identify the contents and packaging operation
- d. blank space for recording the trial ID
- e. directions for use
- f. PI name

- g. protocol number
- h. storage conditions
- i. expiry date
- j. “for clinical trial use only”
- k. “keep out of reach of children”

6.3.5. Returns and Reconciliation

The Investigator/designee is responsible for keeping accurate accountability records for pembrolizumab including the amount dispensed to and returned for each participant and the amount remaining on site at the conclusion of the trial.

Upon completion or termination of the study, it is the Investigators/designee responsibility to ensure all unused and partially used trial medication will be destroyed at the site per local guidelines and provide appropriate records of disposal to the sponsor with a copy being stored in the pharmacy site file.

6.3.6. Dose Selection

The rationale for selection the dose to be used in this trial is provided in Section 1.0 – Background and Rationale. All randomised participants will receive pembrolizumab given as 200mg every 3 weeks by intravenous infusion until progression, intolerance or withdrawal from the trial.

6.3.7. Administration of Pembrolizumab

Details on the preparation and administration of pembrolizumab are provided in the IMP handling guidelines. These guidelines contain specific instructions for pembrolizumab reconstitution, preparation of the infusion fluid, and administration.

6.3.8. Dose Modification

Pembrolizumab will be withheld for drug-related haematological and non-haematological of toxicity \geq Grade 3 including laboratory abnormalities, and severe or life-threatening AEs as per Table 7 below.

Toxicity	Hold Treatment For Grade	Timing for Restarting Treatment	Treatment Discontinuation
Diarrhoea/Colitis	2-3	Toxicity resolves to Grade 0-1.	Toxicity does not resolve within 12 weeks of last dose or inability to reduce corticosteroid to 10 mg or less of prednisone or equivalent per day within 12 weeks.
	4	Permanently discontinue	Permanently discontinue
AST, ALT, or	2	Toxicity resolves to Grade 0-1	Toxicity does not resolve within 12 weeks of last dose.

Increased Bilirubin	3-4	Permanently discontinue (see exception below) ¹	Permanently discontinue
Type 1 diabetes mellitus (if new onset) or Hyperglycemia	T1DM or 3-4	Hold pembrolizumab for new onset Type 1 diabetes mellitus or Grade 3-4 hyperglycemia associated with evidence of beta cell failure.	Resume pembrolizumab when participants are clinically and metabolically stable.
Hypophysitis	2-4	Toxicity resolves to Grade 0-1. Therapy with pembrolizumab can be continued while endocrine replacement therapy is instituted	Toxicity does not resolve within 12 weeks of last dose or inability to reduce corticosteroid to 10 mg or less of prednisone or equivalent per day within 12 weeks.
Hyperthyroidism	3	Toxicity resolves to Grade 0-1	Toxicity does not resolve within 12 weeks of last dose or inability to reduce corticosteroid to 10 mg or less of prednisone or equivalent per day within 12 weeks.
	4	Permanently discontinue	Permanently discontinue
Hypothyroidism		Therapy with pembrolizumab can be continued while thyroid replacement therapy is instituted	Therapy with pembrolizumab can be continued while thyroid replacement therapy is instituted.
Infusion Reaction	3-4	Permanently discontinue	Permanently discontinue
Pneumonitis	2	Toxicity resolves to Grade 0-1	Toxicity does not resolve within 12 weeks of last dose or inability to reduce corticosteroid to 10 mg or less of prednisone or equivalent per day within 12 weeks.
	3-4	Permanently discontinue	Permanently discontinue
	3-4	Permanently discontinue	Permanently discontinue
Renal Failure or Nephritis	2	Toxicity resolves to Grade 0-1	Toxicity does not resolve within 12 weeks of last dose or inability to reduce corticosteroid to 10 mg or less of prednisone or equivalent per day within 12 weeks.
All Other Drug-Related Toxicity²	3 or Severe	Toxicity resolves to Grade 0-1	Toxicity does not resolve within 12 weeks of last dose or inability to reduce corticosteroid to 10 mg or less of prednisone or equivalent per day within 12 weeks.
	4	Permanently discontinue	Permanently discontinue

Note: Permanently discontinue for any severe or Grade 3 drug-related AE that recurs or any life-threatening event.
¹ For participants with liver metastasis who begin treatment with Grade 2 AST or ALT, if AST or ALT increases by greater than or equal to 50% relative to baseline and lasts for at least 1 week then participants should be discontinued.
² Participants with intolerable or persistent Grade 2 drug-related AE may hold study medication at physician discretion. Permanently discontinue study drug for persistent Grade 2 adverse reactions for which treatment with study drug has been held, that do not recover to Grade 0-1 within 12 weeks of the last dose.

Table 8: Dose modification guidelines for drug-related adverse events

If the toxicity does not resolve to Grade 0-1 within 12 weeks after last infusion, trial treatment should be discontinued at the discretion of the investigator. Participants with a laboratory adverse event still at Grade 2 after 12 weeks may continue treatment in the trial only if asymptomatic and controlled. For information on the management of adverse events, see section 7.

Participants who experience a recurrence of the same severe or life-threatening event at the same grade or greater with re-challenge of pembrolizumab should be discontinued from trial treatment.

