	Grade 3	
 Report as ECI within 24 hours Withhold pembrolizumab, may restart if Grade 1 or resolved within 12 weeks Recommend Haematology consultation 	
 IV methylprednisone 125mg or Prednisone 1-2mg/kg p.o. (or equivalent) as appropriate. Permanently discontinue pembrolizumab if corticosteroid dose cannot be reduced to prednisone 10mg or less or equivalent per day within 12 weeks.
	Grade 4	
 Report as ECI within 24 hours Discontinue pembrolizumab Recommend Haematology consultation 	
 IV methylprednisone 125mg or Prednisone 1-2mg/kg p.o. (or equivalent) as appropriate.
Hepatic – Drug induced Liver Injury (DILI). Please refer to ECI guidance for definitions of (DILI)	Grade 1 (Asymptomatic)	
 No action 	
 Intervention not indicated
	Grade 2	
 Report as ECI within 24 hours Withhold Pembrolizumab if AST or ALT >3.0 to 5.0 X ULN and/or total bilirubin is >1.5 to 3.0 X ULN Monitoring Liver function until values return to baseline 	
 0.5-1mg/kg/day methylprednisone 125mg or oral equivalent. LFT grade 1 or less initiate steroid taper for no less than 4 weeks. Consider prophylactic antibiotics and resume pembrolizumab. Permanently discontinue pembrolizumab if dose cannot be reduced to prednisone 10mg or less or equivalent per day within 12 weeks. Permanently discontinue pembrolizumab for patients with liver mets who begin treatment with grade 2 elevation of AST or ALT and AST or ALT increase ≥50% relative to baseline and lasts ≥ 1 week.
	Grade 3	
 Report as ECI within 24 hours Discontinue pembrolizumab if AST or ALT > 5.0 X ULN and/or total bilirubin is >3.0 X ULN Consider consultation and biopsy to establish etiology 	
 High dose IV glucocorticosteroids for 24-48hours. Symptoms grade 1 or less initiate steroid taper for no less than 4 weeks prednisone 1 to 2 mg/kg/day or dexamethasone 4mg every 4 hours. If serum transaminase levels do not decrease or symptoms worsen please refer to additional guidance in the ECI guidance document.

			
 Permanently discontinue pembrolizumab if dose cannot be reduced to prednisone 10mg or less or equivalent per day within 12 weeks.

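### For patients with liver metastases who start with Grade 2 AST/ALT, Table 8 labels a stopping rule as an exception to permanent discontinuation, and Appendix 4 gives no such exception

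*Combined protocol and SAP*

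**What the plan says.** The organ-function table in Section 4.4.1 allows AST and ALT up to 5 x ULN for patients with liver metastases. Appendix 4 places hepatic Grade 2 at above 3.0 and up to 5.0 x ULN, so the trial admits patients who are already at Grade 2.

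Section 6.3.8, in the table captioned Table 8, has a Grade 3-4 row for AST, ALT or bilirubin. Its restart cell reads "Permanently discontinue (see exception below", with a mark leading to footnote 1. The discontinuation cell beside it gives a permanent stop without the mark. Footnote 1 begins "For participants with liver metastasis who begin treatment with Grade 2 AST or ALT, if AST or ALT increases by greater than" and ends by requiring discontinuation if a rise of at least 50% over baseline lasts at least 1 week. It does not say what to do when a patient is short of that threshold.

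The hepatic section of Appendix 4 handles the same ground in two rows. The Grade 2 row contains the same 50% and 1-week rule as a further reason to stop: "Permanently discontinue pembrolizumab for patients with liver mets who begin treatment with grade 2 elevation of AST or ALT and AST or ALT increase". The Grade 3 row says "Discontinue pembrolizumab if AST or ALT > 5.0 X ULN and/or total bilirubin is >3.0 X ULN" and has no exception for these patients.

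On recovery, the Table 8 Grade 2 row allows restart at Grade 0-1, and the Appendix 4 Grade 2 row sets the taper trigger as "LFT grade 1 or less initiate steroid taper for no less than 4 weeks". Text below Table 8 lets asymptomatic, controlled Grade 2 laboratory events continue after 12 weeks.

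**The concern.** An exception to permanent discontinuation should spare somebody, but footnote 1 as worded spares nobody. It names only a condition for stopping. A site that takes the word exception at face value would infer that a value above 5.0 x ULN short of the footnote threshold is a hold. A site that reads Appendix 4, to which Section 6.5.2 sends drug-associated immune-related events of clinical interest, would end pembrolizumab for good. What is at stake is consistent handling across 15 to 24 sites of a stopping rule for a group the trial knowingly admits. A second, smaller problem is that recovery is defined by an absolute grade that these patients did not meet when they entered.

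**Working it through.** **Inputs.** Entry ceiling 5 x ULN (Section 4.4.1). Grade 2 is above 3.0 to 5.0 x ULN and the Grade 3 action applies above 5.0 x ULN (Appendix 4, hepatic rows). Footnote trigger: rise of at least 50% for at least 1 week (Table 8). Dosing every 3 weeks; 12-week limit on recovery (Section 6.3.8). The plan states no figure to reproduce.

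**Step 1: what each place says about a value above 5.0 x ULN in this group.**
- Table 8, restart cell: permanent stop, with an exception.
- Table 8, discontinuation cell: permanent stop.
- Footnote 1: stop if the rise is at least 50% for at least 1 week; otherwise silent.
- Appendix 4, Grade 2 row: the 50% and 1-week rule is an added stop.
- Appendix 4, Grade 3 row: discontinue, no exception.

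**Step 2: is the Appendix 4 stop permanent?** Its plain discontinue instructions for pneumonitis Grade 3-4, colitis Grade 4 and hyperthyroidism Grade 4 all correspond to permanent stops in Table 8. The hepatic Grade 3 row should be read the same way.

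**Step 3: if everyone stops above 5.0 x ULN.** No actions conflict, and only the exception label is wrong. The footnote trigger is 1.5 x baseline, which reaches 5.0 x ULN at a baseline of 5.0 / 1.5 = 3.33 x ULN. On this reading footnote 1 adds a stop only for baselines above 3.0 and up to 3.33 x ULN (triggers of 1.5 x 3.0 = 4.5 up to 5.0 x ULN). Above that baseline, a 50% rise is already past 5.0 x ULN.

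**Step 4: if a true exception is intended.** Table 8 and Appendix 4 disagree for values above 5.0 x ULN and below 1.5 x baseline, which requires a baseline above 3.33 x ULN. The last column is for Step 5: (baseline - 3.0) / baseline.

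| Baseline (x ULN) | 1.5 x baseline | Band of disagreement (x ULN) | Fall needed to reach 3.0 x ULN |
|---|---|---|---|
| 3.5 | 5.25 | 5.0 to 5.25 | 14% |
| 4.0 | 6.0 | 5.0 to 6.0 | 25% |
| 4.5 | 6.75 | 5.0 to 6.75 | 33% |
| 5.0 | 7.5 | 5.0 to 7.5 | 40% |

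Example: 4.0 to 5.5 x ULN is a rise of (5.5 - 4.0) / 4.0 = 37.5%. That is a stop under Appendix 4 and below the footnote threshold. The duration condition adds any value above 5.0 x ULN that has lasted under 1 week, at every Grade 2 baseline. Once a rise of at least 50% has lasted at least 1 week, both places say stop. This reading also leaves no restart condition at Grade 3, because the restart cell itself says permanent stop.

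**Step 5: the restart condition, whichever reading holds.** Under Section 5.3.7 an abnormal screening result is medical history, so a Grade 2 baseline does not itself cause a hold. After a drug-related rise within Grade 2, however, restart at Grade 0-1 means 3.0 x ULN or less. The last column of the table shows how far below the patient's own baseline that lies. A patient who returns promptly to baseline has no written route back before week 12. Doses falling due at weeks 3, 6 and 9 after the last one give at most three missed.

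**The case against.** The strongest reply is that this is one wrong label. The Table 8 discontinuation cell, footnote 1 and both Appendix 4 rows are all worded as stops, and only the parenthetical in the restart cell points elsewhere. The bands in Step 4 depend entirely on a reading that the weight of the text does not favour. That largely stands. It is not conclusive, because on that reading footnote 1 does work only for baselines above 3.0 and up to 3.33 x ULN, and its label remains unexplained.

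Three further inferences are tempting, and the documents do not support them:
- A reader might infer that the Appendix 4 Grade 3 stop is provisional, because the row later says "Permanently discontinue pembrolizumab if dose cannot be reduced to prednisone 10mg or less or equivalent per day within 12 weeks". The same sentence stands in the hepatic Grade 2 row. It also reaches hyperthyroidism Grade 4, a permanent stop in Table 8, through the instruction to manage as Grade 3. It reads as carried-over text, not as evidence of a prior hold.
- A reader might take the opening of Section 6.3.8, "Pembrolizumab will be withheld for drug-related haematological and non-haematological of toxicity" of Grade 3 or above, as pointing to a hold. That sentence introduces the whole table, including rows that are plainly permanent stops.
- A reader might treat the unmarked cell beside the marked one as a contradiction. One footnote mark can serve a whole row.

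On restart, some of the three doses would probably be missed anyway, since Appendix 4 calls for steroids and a taper of at least 4 weeks. Sections 5.3.7 and 7.1.3 recognise investigator judgement, and 7.1.3 recognises return to baseline, but neither replaces the Grade 0-1 condition.

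Finally, Appendix 4 refers sites elsewhere: "If serum transaminase levels do not decrease or symptoms worsen please refer to additional guidance in the ECI guidance document". That document was not available for this review, so it may contain a resolving instruction.

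**Conclusion.** The inconsistency is real but minor. Most operative text favours stopping every patient above 5.0 x ULN, and on that reading the only error is the exception label in Table 8. If an exception is intended, Table 8 and Appendix 4 conflict within the limits in Step 4. Nothing in the protocol settles which is meant: for hepatitis, Section 6.5.2 says only to withhold or discontinue by severity. The Grade 0-1 restart condition is a separate defect under either reading, eased only by the 12-week clause.

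A reader might infer that some patients would go on being dosed above 5.0 x ULN. The documents do not support that, because Section 6.3.8 withholds drug for drug-related laboratory toxicity of Grade 3 or above; the open question is only hold or permanent stop. Nor is there a basis for claiming an effect on the week-12 response comparison. The protocol does not give the number of patients affected; it is assumed to be small, since a patient needs liver metastases, Grade 2 AST/ALT at entry and a drug-related rise. Section 6.5.2 also asks for immediate discussion of Grade 2 or higher immune-related events with the chief investigator or designee. That reduces divergence between sites without supplying the rule.

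**What to change.** State one rule in both places.

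- **Default.** Delete the exception parenthetical from the Table 8 Grade 3-4 row, keep footnote 1 as an added stopping rule, and write *permanently discontinue* in the Appendix 4 hepatic Grade 3 row.
- **If an exception is intended.** Write it in both tables: pembrolizumab is held above 5.0 x ULN while the rise is under 50% of baseline or has lasted under 1 week, and is stopped permanently once both limits are reached.
- **In either case.** For these patients, make the restart condition in Table 8 and the taper trigger in Appendix 4 *Grade 0-1 or baseline*.

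The cost is a few words in the Table 8 AST/ALT rows and the Appendix 4 hepatic Grade 2 and Grade 3 rows. Baseline AST and ALT are already collected at screening, so no new testing is needed. The choice between the first two options is a clinical one for the sponsor, who should also check the wording against the guidance document on events of clinical interest.
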